**Table 4: NKTR-102 Dose Modifications**

Toxicity NCI CTCAE Grade	During a Cycle	Dose Modifications for Day 1 of New Cycle
Neutropenia / Febrile Neutropenia		
Grade 1 (ANC <1500/mm  )		Maintain dose level.
Grade 2 (ANC ≥1000/mm  , <1500/mm  )	Consider growth factor support in accordance with local guidelines.	
If present on a treatment day, hold therapy until toxicity resolves to ANC ≥1500/mm^3.
 
 
• ↓ 1 dose level after 1st occurrence (provided screening ANC > 2000/mm^3); do not reduce dose for Grade 2 neutropenia if screening ANC was ≥ 1500 and < 2000/mm^3. Consider prophylactic growth factor therapy.
 
• ↓ 1 dose level after 2nd occurrence. Consider prophylactic growth factor therapy.
 
 
Provided that adequate supportive care has been given to the patient, and the investigator believes it is in the best interest of the patient, retreatment may be attempted for a 3rd episode of Grade 2 ANC.

Grade 3 (ANC ≥500/mm  , <1000/mm  )	Consider growth factor support in accordance with local guidelines.	
If present on a treatment day, hold therapy until toxicity resolves to ANC ≥ 1500/mm^3.
 
 
• ↓ 1 dose level after 1st occurrence. Use prophylactic growth factor therapy.
 
• ↓ 1 dose level after 2nd occurrence. Use prophylactic growth factor therapy.
 
 
Provided that adequate supportive care has been given to the patient, and the investigator believes it is in the best interest of the patient, retreatment may be attempted for a 3rd episode of Grade 3 ANC.

Grade 4 (ANC <500/mm  )	Consider growth factor support in accordance with local guidelines. Consider use of antibiotic (oral fluoroquinolones) even in the absence of fever or diarrhea.	
If present on a treatment day, hold therapy until toxicity resolves to ANC ≥ 1500/mm^3.
 
 
• ↓ 1 dose level after 1st occurrence. Use prophylactic growth factor therapy.
 
• ↓ 1 dose level after 2nd occurrence. Use prophylactic growth factor therapy.
 
 
Discontinue NKTR-102 after 3rd occurrence.

Toxicity NCI CTCAE Grade	During a Cycle	Dose Modifications for Day 1 of New Cycle
Febrile Neutropenia Grade 3 or 4 (ANC <1000/mm  with a single temperature of ≥ 38.3°C (101°F) or a sustained temperature of ≥ 38°C (100.4°F) for more than one hour	Treat as appropriate (eg, growth factor support; antibiotics); consider hospital admission. Patients should be hospitalized for IV antibiotic therapy if sepsis is suspected.	Retreatment must be delayed until the toxicity is Grade ≤ 1. 
 
• ↓ 1 dose level after 1st occurrence. Use prophylactic growth factor therapy.
 
• ↓ 1 dose level after 2nd occurrence. Use prophylactic growth factor therapy.
 
 Discontinue NKTR-102 after 3rd occurrence.
Thrombocytopenia		
Grade 1 or 2		Maintain dose level.
Grade 3 (Platelets ≥ 25, <50K)	Consider platelet transfusion if active bleeding. Following platelet transfusion, retreatment must be delayed for 7 days and patient must meet retreatment criteria prior to dosing.	If present on a treatment day, hold therapy until toxicity resolves to platelets ≥ 50K. 
 
• ↓ 1 dose level after 1st occurrence.
 
• ↓ 1 dose level after 2nd occurrence.
 
 Provided that adequate supportive care has been given to the patient, and the investigator believes it is in the best interest of the patient, retreatment may be attempted for a 3rd episode of Grade 3 thrombocytopenia.
Grade 4 (Platelets < 25K)	Consider platelet transfusion if platelets ≤10K or with active bleeding. Following platelet transfusion, retreatment must be delayed for 7 days and patient must meet retreatment criteria prior to dosing.	If present on a treatment day, hold therapy until toxicity resolves to platelets ≥ 50K. 
 
• ↓ 1 dose level after 1st occurrence.
 
• ↓ 1 dose level after 2nd occurrence.
 
 Discontinue NKTR-102 after 3rd occurrence.
Anemia		
Grade 1 or 2		Maintain dose level
Grade 3 Hgb <8	Provide erythropoietin-stimulating agents or transfusion as appropriate.	If present on a treatment day, hold therapy until toxicity resolves to Hgb >8 
 
• ↓ 1 dose level after 1st occurrence.
 
• ↓ 1 dose level after 2nd occurrence.
 
 Provided that adequate supportive care has been given to the patient, and the investigator believes it is in the best interest of the patient, retreatment may be attempted for a 3rd episode of Grade 3 anemia

Toxicity NCI CTCAE Grade	During a Cycle	Dose Modifications for Day 1 of New Cycle
Grade 4 Hgb<6.5	Consider erythropoietin-stimulating agents or transfusion as appropriate.	
 
• If present on a treatment day, hold therapy until toxicity resolves to Hgb >8
 
• ↓ 1 dose level after 1st occurrence.
 
• ↓ 1 dose level after 2nd occurrence.
 
 Discontinue NKTR-102 after 3 rd occurrence
Diarrhea		
Any Grade	Institute supportive care upon first loose stool. (Unless contraindicated, use loperamide). Monitor bowel function; if diarrhea continues with 1 st supportive care agent, consider switching to a 2 nd agent or add a 2 nd agent (unless contraindicated, use diphenoxylate/atropine). Monitor for dehydration, electrolyte abnormalities; correct if present. Administer antibiotic therapy (oral fluoroquinolones) if the patient develops ileus, fevers, or Grade 3/4 neutropenia. Patients should be hospitalized for IV antibiotic therapy if there is evidence of colitis or ileus even in the absence of neutropenia or fever. If diarrhea is worsening, octreotide may be attempted. Monitor bowel function for continued need for supportive care. Stop supportive care after the patient is 48 hr without diarrhea.	Confirm with the patient that diarrhea is no longer present for ≥ 7 days without having received supportive care prior to retreatment. Treatment may be delayed up to 28 days; after this, contact Medical Monitor.
Grade 1		Maintain dose level; consider prophylactic anti-diarrheal supportive care
Grade 2		
 
• ↓ 1 dose level after 1st occurrence; use prophylactic anti-diarrheal supportive care
 
• ↓ 1 dose level after ≥ 2nd occurrence; use prophylactic anti-diarrheal supportive care
 
 Provided that adequate supportive care has been given to the patient, retreatment may be attempted for a 3 rd episode of Grade 2 diarrhea (re-instruct the patient on supportive care).

Toxicity NCI CTCAE Grade	During a Cycle	Dose Modifications for Day 1 of New Cycle
Grade 3/4		
 
• ↓ 2 dose levels after 1st occurrence; use prophylactic anti-diarrheal supportive care
 
 Provided that adequate supportive care has been given to the patient, retreatment may be attempted for a 2nd episode of Grade 3 diarrhea (re-instruct the patient on supportive care).
Dehydration		
Grade 1: Increased oral fluids indicated; dry mucous membranes; diminished skin turgor	Consider anti-emetic or anti-diarrheal supportive care	Maintain dose level; consider prophylactic anti-diarrheal or anti-emetic supportive care
Grade 2: IV fluids indicated <24 hours	Use anti-emetic and/or anti-diarrheal supportive care	Maintain dose level or ↓ 1 dose level after 1 st occurrence; use prophylactic anti-emetic or anti-diarrheal supportive care. 
 
• ↓ 1 dose level after ≥ 2nd occurrence; use prophylactic anti-emetic or anti-diarrheal supportive care.
 
 Provided that adequate supportive care has been given to the patient, retreatment may be attempted for a 3 rd episode of Grade 2 dehydration (re-instruct the patient on supportive care).
Grade 3: IV fluids or hospitalization Indicated; Grade 4: Life-threatening consequences; urgent intervention indicated	Use anti-emetics, anti-diarrheal supportive care, and/or IV fluids as appropriate. Consider hospital admission.	Treatment must be delayed until the toxicity recovered to baseline or Grade < 1. 
 
• ↓ 2 dose levels after 1st occurrence; use prophylactic anti-emetic or anti-diarrheal supportive care.
 
 Provided that adequate supportive care has been given to the patient, retreatment may be attempted for a 2 nd episode of Grade 3 dehydration (re-instruct the patient on supportive care). NKTR-102 must be discontinued for a 2 nd episode of Grade 4 dehydration.
Nausea/Vomiting/Abdominal Pain		
Grade 1/2	Consider anti-emetic supportive care.	Maintain dose level; consider prophylactic anti-emetic supportive care.

Toxicity NCI CTCAE Grade	During a Cycle	Dose Modifications for Day 1 of New Cycle
Grade 3	Use anti-emetic supportive care. Consider administration of IV fluids.	Treatment must be delayed until the toxicity recovered to baseline or Grade < 1 
 
• ↓ 1 dose level after 1st occurrence; use prophylactic anti-emetic supportive care
 
• ↓ 1 dose level after 2nd occurrence; use prophylactic anti-emetic supportive care.
 
 Provided that adequate supportive care has been given to the patient, retreatment may be attempted for a 3 rd episode of Grade 3 nausea/vomiting/abdominal pain
Grade 4	Use anti-emetic supportive care and IV fluids.	Treatment must be delayed until the toxicity recovered to baseline or Grade < 1 2 dose levels after 1 st occurrence; use prophylactic anti-emetic supportive care Discontinue NKTR-102 after 2 nd occurrence
Other drug-related non-hematologic toxicities (except fatigue/asthenia and alopecia)		
Grade 1/2	Consider supportive care as appropriate	Maintain dose level (for Grade 2 toxicity, the Investigator may use discretion to ↓ 1 dose level after 1 st occurrence depending on the nature of the toxicity). If recurrent Grade 2 toxicity Investigator may choose to ↓ 1 dose level; continue supportive care.
Grade 3	Use supportive care as indicated	Treatment must be delayed until the toxicity has resolved or returned to baseline ↓ 1 dose level after 1 st occurrence; supportive care as appropriate ↓ 1 dose level after 2 nd occurrence Provided that adequate supportive care has been given to the patient, retreatment may be attempted for a 3 rd episode of Grade 3 other drug-related non-hematological toxicities (except fatigue, asthenia)
Grade 4	Use supportive care as indicated. Consider hospital admission.	Treatment must be delayed until the toxicity recovered to baseline or Grade < 1 ↓ 2 dose levels after 1 st occurrence. Discontinue NKTR-102 after 2 nd occurrence

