## 6.7 Dose Modifications and Delays

All adverse events (AEs) will be assessed according to the NCI-CTCAE version 4.0. In the event of multiple toxicities, dose delays and modifications should occur in accordance with the worst toxicity observed.

Specific dose modifications for NKTR-102 will be made for diarrhea, dehydration, hematological, and other non-hematological toxicities. Dose delays may be permitted between cycles.

Prior to initiation of subsequent NKTR-102 cycles, subjects must meet requirements with respect to hematopoietic function (hemoglobin  $\geq 8.0$  g/dL or 80 g/L; ANC  $\geq 1.5 \times 10^9$ /L; platelets  $\geq 75 \times 10^9$ /L). Diarrhea must be fully resolved to NCI-CTCAE Grade 0 (a return to normal bowel movement habits) for at least 7 days without supportive antidiarrheal measures prior to retreatment. Any treatment-related non-hematologic toxicities must have resolved to baseline or Grade 1.

If the subject fails to meet the criteria for re-treatment, treatment may be delayed, followed by an additional evaluation to determine feasibility of retreatment. Initiation of subsequent doses may be delayed for a maximum of 28 days to allow recovery from any toxicity to permit retreatment. Subjects whose treatment delays are  $\geq 14$  days but  $\leq 28$  days due to a drug-related toxicity must initiate their next treatment cycle with a dose reduction. Subjects who require  $> 28$  days delay due to unresolved toxicity must be withdrawn from treatment, unless, in the Investigator's opinion, continuing in the study is of benefit for the subject. In this case, the continuation of treatment must be discussed with the Medical Monitor and the reason for continuation must be approved and documented.

Subjects from Protocol 12-102-13 with impaired liver function who are entering the extension study will receive the same dose as that received in the 12-102-13 study. Investigators may choose to reduce the dose of NKTR-102 for either drug-related or non-drug related Grade 3 or higher liver dysfunction only after approval from Nektar Medical Monitor.

Supportive care may be implemented in order to treat diarrhea, nausea, vomiting, anorexia, myelosuppression, and/or other AEs. Dose delays may be implemented to permit recovery if a subject is demonstrating clinical benefit, but with repeated Grade 2 toxicities that would otherwise mandate withdrawal.

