Dose reductions may also be implemented for subjects who experience recurrent or specific severe toxicities (see [Table 4](#)). NKTR-102 doses for an individual subject may be reduced by 25 mg/m^2 based on conditions listed in [Table 4](#). Subjects should be discontinued from the study treatment if toxicity would indicate more than 2 dose reductions. Dose re-escalation for NKTR-102 is not permitted.

- For subjects entering this study at a starting dose of 145 mg/m^2: dose reductions to 120 mg/m^2, then to 95 mg/m^2 may occur based on conditions listed in [Table 4](#).
- For subjects (i.e., from Protocol 12-102-13) entering this study at a starting dose of 120 mg/m^2: dose reductions to 95 mg/m^2, then to 70 mg/m^2 may occur based on conditions listed in [Table 4](#).
- For subjects (i.e., from Protocol 12-102-13) entering this study at a starting dose of 95 mg/m^2: dose reduction to 70 mg/m^2 may occur based on conditions listed in [Table 4](#).
- For subjects (i.e., from Protocol 12-102-13) entering this study at a starting dose of 50 mg/m^2: dose reduction should be approved by Medical Monitor.
- [Table 4](#) provides instructions regarding dose modification.
- DURING A CYCLE: [Table 4](#)/Column 2 describes the recommended guidelines for management and supportive care during a cycle of therapy.
- INITIATION OF A SUBSEQUENT CYCLE: [Table 4](#)/Column 3 describes the recommended dose modifications for Day 1 in subsequent cycles of therapy. All dose modifications in a new cycle should be based on the worst toxicity observed in the previous cycle and the dose reduction will be relative to the Day 1 dose of the previous cycle.

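### Table 4 ends the hold for Grade 3 or 4 thrombocytopenia at platelets ≥ 50K, below the 75 × 10⁹/L that Section 6.7 requires of every subject before redosing, and nothing says which value prevails when no transfusion was given

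*Protocol*

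**What the plan says.** For later cycles, Protocol Section 6.7 states: "Prior to initiation of subsequent NKTR-102 cycles, subjects must meet requirements with respect to hematopoietic function". It then lists hemoglobin ≥ 8.0 g/dL, ANC ≥ 1.5 × 10⁹/L and platelets ≥ 75 × 10⁹/L. The rule is mandatory and has no transfusion condition. Inclusion criterion 7 (Section 5.1) uses the same three values.

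Table 4, column 3, gives the same instruction for Grade 3 (25K to below 50K) and Grade 4 (below 25K) thrombocytopenia: "If present on a treatment day, hold therapy until toxicity resolves to platelets ≥ 50K". The only mention of the retreatment criteria in these two rows is in column 2: "Following platelet transfusion, retreatment must be delayed for 7 days and patient must meet retreatment criteria prior to dosing".

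Section 6.7 introduces column 3 as the part of the table that "describes the recommended dose modifications for Day 1 in subsequent cycles of therapy". On timing it says: "Initiation of subsequent doses may be delayed for a maximum of 28 days to allow recovery from any toxicity to permit retreatment".

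**The concern.** Two rules in one section give different platelet values for the same decision. A site that looks up the thrombocytopenia row finds 50K. A site that reads the paragraph above the table finds 75. The subjects concerned have just had a Grade 3 or 4 platelet count on a cytotoxic drug whose active metabolite has an apparent half-life of about 40 days (Sections 2.1 and 2.1.2.3). Redosing at 50 to below 75 would follow the table row while breaching the mandatory rule. At stake are dosing safety and consistent practice across up to 100 sites.

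**Working it through.** No sample size or error rate is involved, so the check compares thresholds in common units.

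**Units.** 1K per mm³ = 1 × 10⁹/L, so 50K = 50 × 10⁹/L, and 1500/mm³ = 1.5 × 10⁹/L. Table 4 gives hemoglobin without units; g/dL is assumed.

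**Numeric release values in the hematology rows of Table 4**

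| Rows | Section 6.7 | Table 4 | Difference |
|---|---|---|---|
| ANC, Grades 2, 3, 4 | ≥ 1.5 | ≥ 1.5 | 0 |
| Platelets, Grades 3, 4 | ≥ 75 | ≥ 50 | 75 − 50 = 25 |
| Hemoglobin, Grades 3, 4 | ≥ 8.0 | > 8 | only at exactly 8.0 |

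The ANC rows use the same form of words ("hold therapy until toxicity resolves to ANC" ≥ 1500/mm³) and land on the Section 6.7 floor. Of the seven numeric rows, only the two platelet rows fall below it: 50/75 = 0.67, a shortfall of 25/75 = 33.3%.

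**Counts tested against both rules (× 10⁹/L)**

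| Platelets | Table 4 hold over? | Section 6.7 met? |
|---|---|---|
| 49 | no | no |
| 50 | yes | no |
| 60 | yes | no |
| 74 | yes | no |
| 75 | yes | yes |

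The rules disagree from 50 to below 75 and nowhere else.

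**Does another place settle it?**
- By the table's own limit for Grade 3, a subject at 50 to below 75 is in the Grade 1 or 2 row. That row keeps the dose unchanged and mentions no hold.
- Section 6.10 restates the retreatment value for ANC only.
- Section 7.2 requires a platelet result before each dose but gives no cut-off, although it does repeat the diarrhea and non-hematologic criteria.
- When criteria are not met, Section 6.7 says that treatment may be delayed, which is permissive wording.

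**Other differences between text and table.** Febrile neutropenia is released by grade: "Retreatment must be delayed until the toxicity is Grade ≤ 1". For non-hematologic events Section 6.7 says: "Any treatment-related non-hematologic toxicities must have resolved to baseline or Grade 1". Several Table 4 rows ask for more: recovery to baseline or below Grade 1 for Grade 3 or 4 dehydration, for example. These bear on how the fix is worded, because a general sentence must not loosen them.

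**How many subjects.** No thrombocytopenia rate is given. It is absent from Table 1 (Phase 3 events above 20%, N = 425). If such events were coded under one term, that means at most 0.20 × 425 = 85 patients at any grade, which is a loose ceiling. It is also absent from Table 2, which lists events leading to discontinuation in more than one patient in either arm.

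**The case against.** The strongest reply is that the two rules can both be obeyed. Ending a hold at 50K is not an instruction to dose at 50K, and it does not waive a mandatory rule in the same section. Column 3 is introduced as recommended, whereas the retreatment rule is an obligation. The Grade 1 or 2 row, with no hold of its own, makes sense only if Section 6.7 acts as a separate gate. On this view 75 always governs, and an unsafe dose requires a site to disregard a plain requirement.

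Most of this stands: 75 is the better reading. But on that reading 50K never decides when anyone may be dosed, so the number is either without function or misleading. A reader has some reason to be misled, since the ANC rows state the actual retreatment value and the hemoglobin rows all but do so. The pointer to the retreatment criteria in the platelet rows covers only transfused subjects.

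A reader might go further and infer that the protocol sets no floor of 75 for non-transfused subjects, or that Table 4 authorizes dosing them at 50K. The documents support neither. Section 6.7 applies 75 to every subject, transfused or not. What is missing is narrower: a statement that 75 prevails over the table's release value when no transfusion was given.

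**Conclusion.** The inconsistency is real and minor. Table 4 releases the hold 25 × 10⁹/L below the Section 6.7 floor in two rows, and the protocol leaves the site to infer that the floor still applies. The consequence is confined to dosing safety and protocol compliance in subjects held for Grade 3 or 4 thrombocytopenia who have recovered to 50 to below 75. Their number cannot be derived from the documents. It is probably small, given the absence of thrombocytopenia from Tables 1 and 2; this assumes that the Phase 3 experience carries over to longer exposure. No endpoint, test or sample size changes.

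Taking 75 as the intended value rests on the mandatory wording of Section 6.7, the matching entry criterion, and the agreement of the ANC rows, and nearly of the hemoglobin rows, with Section 6.7.

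**What to change.** Change ≥ 50K to ≥ 75K in the Grade 3 and Grade 4 thrombocytopenia rows, which brings the gap to 75 − 75 = 0. Add before Table 4: *The Section 6.7 retreatment criteria apply in addition to Table 4; where they differ, the stricter applies.* Do not lower the Section 6.7 value. The added sentence loosens no row: the stricter non-hematologic releases stay in force, and the febrile neutropenia row also takes the ANC floor.

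The cost is a wording amendment of two cells and one sentence, with no new visit, procedure or data. The downside is that sites that would have dosed at 50 to below 75 will hold longer, as Section 6.7 already requires. Longer holds have consequences under that section:
- A drug-related delay of 14 to 28 days requires a dose reduction at the next cycle.
- Subjects should stop treatment if toxicity would call for more than two reductions.
- A delay beyond 28 days for unresolved toxicity means withdrawal from treatment by default. The exception is when the Investigator judges continuation to be of benefit, discusses it with the Medical Monitor, and the reason is approved and documented.

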## 6.8 Antidiarrheal Therapy

Subjects may experience diarrhea following administration of NKTR-102.

To date, *early-onset diarrhea* (occurring during or shortly after infusion of study drug) has rarely been seen with NKTR-102 administration. It is usually transient and only infrequently severe. It may be accompanied by symptoms of rhinitis, increased salivation, miosis, lacrimation, diaphoresis, flushing, and intestinal hyperperistalsis that can cause abdominal cramping. Early diarrhea and other cholinergic symptoms may be prevented or ameliorated by administration of atropine (0.25 to 1 mg subcutaneous or IV), however, routine prophylactic use of atropine is not recommended.

Late onset diarrhea (occurring more than 24 hours after the infusion) can be life-threatening, because it may be prolonged and may lead to dehydration, hypotension, and renal failure. In the BEACON study, 9.6% of patients reported Grade 3 diarrhea. Among those patients, the median time to onset of Grade 2 or higher diarrhea was 40 days, and the median onset for Grade 3 diarrhea was 43 days. In addition, the median time to resolution of Grade 2 or higher diarrhea was 3.5 days and the median time to resolution of Grade 3 diarrhea was 6 days. There were no incidents of Grade 4 diarrhea.

It should be noted in the patient's medical record whether the subject is currently receiving anti-diarrhea supportive care and the date of the last episode of diarrhea/loose stool.

Diarrhea must be treated promptly with anti-diarrheal therapy; loperamide is recommended. Each subject must be instructed to immediately begin taking anti-diarrheal therapy at the very first episode of poorly formed or loose stools or the earliest onset of bowel movements that are more frequent than normally expected for the subject. Subjects with diarrhea must be carefully monitored, should be given adequate fluid and electrolyte replacement if they become dehydrated, and antibiotic support if they develop ileus, fever, or severe neutropenia.

- Prophylactic antidiarrheal medications must not be used as they can confound the evaluation of recovery to Grade 0 (a return to normal bowel movement habits) and monitoring of diarrhea AEs in subjects receiving NKTR-102.
- Each subject will be instructed to start taking anti-diarrheal therapy (i.e., loperamide) for diarrhea at the first episode of poorly formed or loose stools or the earliest onset of bowel movements more frequent than normally expected for the subject.

- One dosage regimen for loperamide used in clinical trials consisted of the following (Note: This dosage regimen exceeds the usual dosage recommendations for loperamide.): **4 mg at the first onset of diarrhea and then 2 mg every 2 hours until the subject is diarrhea-free for at least 12 hours.** Loperamide is not recommended to be used for more than 48 consecutive hours at these doses, because of the risk of paralytic ileus. During the night, the subject may take 4 mg of loperamide every 4 hours.
- The use of drugs with stimulant laxative properties should be avoided because of the potential for exacerbation of diarrhea.
- **Subjects will be instructed to report the following:** diarrhea for the first time during the infusion of NKTR-102; black or bloody stools; symptoms of dehydration such as lightheadedness, dizziness, or faintness; inability to take fluids by mouth due to nausea or vomiting; inability to get diarrhea under control within 24 hours; or fever or evidence of infection.

An Institutional Review Board (IRB)-approved subject instruction sheet on the management of diarrhea will be provided to all the subjects.

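### Section 6.8 bans prophylactic antidiarrheals outright, three Table 4 diarrhea entries direct their use, and no text says which governs

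*Protocol*

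**What the plan says.** Protocol Section 6.8 (Antidiarrheal Therapy) gives the rule in a bullet: "Prophylactic antidiarrheal medications must not be used as they can confound the evaluation of recovery to Grade 0". The same sentence adds a second reason, that prophylaxis can confound the monitoring of diarrhea adverse events. The bullet names no group of subjects and no cycle to which it does not apply.

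Table 4 (NKTR-102 Dose Modifications), in the column for Day 1 of a new cycle, tells sites after Grade 2 and after Grade 3/4 diarrhea to "use prophylactic anti-diarrheal supportive care". Section 6.7 says that this column "describes the recommended dose modifications for Day 1 in subsequent cycles of therapy". It does not mention the ban, and 6.8 does not mention Table 4.

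One related rule is not in dispute. Section 6.7 requires diarrhea to be at Grade 0 "for at least 7 days without supportive antidiarrheal measures prior to retreatment", and the Any Grade diarrhea row of Table 4 agrees: "Confirm with the patient that diarrhea is no longer present for ≥ 7 days without having received supportive care prior to retreatment".

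**The concern.** A site whose subject has had Grade 2 or worse diarrhea faces a prohibition in one place and a direction in another, for the same drug class in the same cycle. Whichever it follows, it departs from the other, and Section 11.1 does not allow departures from the protocol without an approved amendment, except to remove an immediate hazard.

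The Synopsis names the incidence and duration of toxicities as the primary endpoint, and Section 2.1.2.4 describes diarrhea as the most common clinically significant toxicity. Section 6.8 itself says that prophylaxis can confound diarrhea monitoring. If some sites give it after an episode and others withhold it, the diarrhea tables will mix two management policies.

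**Working it through.** No sample size, power or error rate is involved. The check sets the two texts side by side and then looks for anything that reconciles them.

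**Step 1. Table 4 entries that name prophylactic antidiarrheals (new-cycle column).**

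| Row | Entries | Instruction | Can it be followed together with 6.8? |
|---|---|---|---|
| Diarrhea Grade 1 | 1 | "Maintain dose level; consider prophylactic anti-diarrheal supportive care" | Yes, by considering and declining |
| Diarrhea Grade 2 (1st; 2nd or later) | 2 | "use prophylactic anti-diarrheal supportive care" | No |
| Diarrhea Grade 3/4 (1st) | 1 | "use prophylactic anti-diarrheal supportive care" | No |
| Dehydration Grade 1 | 1 | "consider prophylactic anti-diarrheal or anti-emetic supportive care" | Yes, by declining or choosing an anti-emetic |
| Dehydration Grade 2 (1st; 2nd or later) | 2 | "use prophylactic anti-emetic or anti-diarrheal supportive care" | Yes, by choosing an anti-emetic |
| Dehydration Grade 3/4 (1st) | 1 | "use prophylactic anti-emetic or anti-diarrheal supportive care" | Yes, by choosing an anti-emetic |

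Diarrhea rows: 1 + 2 + 1 = 4. Dehydration rows: 1 + 2 + 1 = 4. Total 8. Direct conflict with 6.8: 2 + 1 = 3. Offered as an option although 6.8 forbids it: 8 − 3 = 5.

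**Step 2. Search for a reconciling rule.** Sections 6.7, 6.8, 6.10, 6.11 and 7.2, the Synopsis and the SAP contain no order of precedence and do not limit 6.8 to subjects who have never had diarrhea.

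**Step 3. Does the reason given in 6.8 settle its scope?** Recovery to Grade 0 can be evaluated only in someone who has had diarrhea. The stated reason therefore applies after an episode at least as well as before one, and cannot be used to confine the ban to primary prophylaxis.

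**Step 4. What does not depend on the choice?** Treatment at the first loose stool (6.8, 6.11.1, Table 4), the dose reductions in Table 4, and 7 days free of diarrhea and of antidiarrheals before retreatment (6.7, 7.2, Table 4) apply under either text.

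**Step 5. Which results are exposed?** A subject who triggers a Table 4 diarrhea entry during this study has already been counted once for diarrhea. The parts most open to variation are therefore repeat episodes, worst grade and duration. Incidence itself is more exposed where dehydration, or an episode in the original study, is taken as the trigger.

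**Step 6. How often could it arise? (Illustration only.)** Table 1 reports Grade 2 diarrhea in 14.8% and Grade 3 in 9.6% of BEACON patients: 14.8 + 9.6 = 24.4%. Applied to the planned maximum of 150 subjects, 0.244 × 150 = 36.6, or about 37. At half that rate it is about 18 (0.122 × 150 = 18.3), and at one and a half times about 55 (0.366 × 150 = 54.9). The true rate could be lower, because these subjects have already tolerated the drug, or higher, because exposure is longer. This counts subjects who might meet the conflict. It does not measure the effect on the tables.

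**The case against.** The best defence is that 6.8 concerns primary prophylaxis and Table 4 concerns prophylaxis after an episode. There is real support for it. Every entry in the new-cycle column follows a toxicity that has already occurred. Section 6.10 opens with a flat ban on prophylactic growth factor and then gives later-cycle prophylaxis as an example of permitted use, in line with the neutropenia rows of Table 4. Section 6.11 gives investigators wide latitude over supportive care, and the prohibited list in 6.11.2 does not name prophylactic antidiarrheals. This is probably what the sponsor meant. It still has to be inferred: 6.10 writes out its exception, and 6.8 has none.

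A reader might take Section 6.11.1 as proof of a full ban, since it mentions antiemetic prophylaxis but early interventional therapy for diarrhea. That goes too far, because the wording introduces examples and not a closed list. A reader might equally treat Table 4 as optional because 6.7 calls the column recommended. But 6.7 also says that specific modifications will be made for diarrhea, so that word does not settle precedence.

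It is also fair to say that the consequence is modest. The primary objective is access, there is no comparator, and the analysis is descriptive. Antidiarrheal use should be traceable: 6.8 asks for current antidiarrheal care to be noted in the medical record, and 6.11 sends concomitant medications to the eCRF. All of this stands. It limits the weight of the point without removing the contradiction.

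**Conclusion.** The contradiction is real and should be fixed. Three Table 4 entries cannot be followed together with Section 6.8, and no text decides between them. A reader might infer eight contradictions from the eight entries, but five can be met without an antidiarrheal and are only inconsistent in spirit.

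A reader might also infer that subjects are put at risk, or that the primary endpoint is biased by a known amount. The documents support neither. The main safeguards hold under both texts, and nothing in the documents allows the effect on recorded diarrhea to be estimated. What remains is possible variation between sites in managing and recording the most common toxicity, carried into descriptive tables. That conclusion assumes that some sites would follow 6.8 and others Table 4, which the wording allows but does not show.

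Two nearby mismatches are separate matters, and this point does not rest on them: the platelet values for resuming treatment (50K in Table 4, 75 × 10^9/L in 6.7), and the statement in SAP 7.4.1 that concomitant medications are not collected.

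**What to change.** Reword the 6.8 bullet along these lines:

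> Prophylactic antidiarrheals must not be used before a subject's first episode of diarrhea; after an episode, follow Table 4 for prophylactic antidiarrheal care in later cycles, subject to the 7-day rule in Section 6.7.

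The instruction should be to follow Table 4. Saying only that prophylaxis is allowed would leave a permissive sentence beside a directive table.

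The clinical team needs to decide whether an episode in the original study counts as the first. Section 6.3 lets symptoms in that study justify prophylactic anti-emetics, but nothing comparable exists for antidiarrheals, so this is a clinical choice and not a drafting correction.

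If a full ban is intended, leave 6.8 as it is, delete prophylactic antidiarrheals from the eight Table 4 entries, and keep prophylactic anti-emetics in the dehydration rows.

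The cost is one protocol amendment with IRB/IEC approval (Section 13.1), and possibly a revised subject instruction sheet on diarrhea (Section 6.8). No visits, tests or subjects are added.
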